### 2.3.2.3 Maintenance Treatment Period

At Week 16 subjects in the bimekizumab 320mg treatment arm will be re-randomized 1:2 to receive bimekizumab 320mg Q4W or bimekizumab 320mg Q8W. To maintain the blind after re-randomization, subjects in the bimekizumab 320mg Q8W treatment arm will receive placebo at Weeks 20, 28, 36, and 44. Subjects in the secukinumab arm will continue to receive secukinumab 300mg Q4W.

Subjects will be classified as completing the maintenance treatment period if they complete the Week 48 Visit without early withdrawal from the study or if they start treatment in the Open-Label period. The start of the Open-Label extension period marks the end of the maintenance treatment period for subjects opting to participate in the OLE period. Otherwise the end of the maintenance period is marked by the Week 48 visit.

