## **2.4 Determination of sample size**

A total of 700 subjects will be randomly assigned in a 1:1 ratio at Baseline to one of the following treatment groups:

- Bimekizumab 320mg (350 subjects)
- Secukinumab 300mg (350 subjects).

The primary efficacy analysis is based on the comparison of bimekizumab to secukinumab for the primary efficacy variable of PASI100 response at Week 16. The assumed responder rates for PASI100 at Week 16 are 60% and 44% for bimekizumab and secukinumab, respectively. The assumed responder rate for bimekizumab is based on the Phase 2b PS0010 data. The assumptions related to the responder rates for secukinumab are based on those observed in the CLEAR study (Thaçi et al, 2015). The power to show statistical superiority of bimekizumab relative to secukinumab under these assumptions is 98% for the primary endpoint. The power for the non-inferiority comparison (with 10% non-inferiority margin) under these assumptions is >99%.

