where  $N_{AE}$  is the total number of AEs,  $T_{Risk(i)}$  is the time at risk for then  $i^{th}$  subject, and N is the total number of subjects at risk.

No confidence interval will be computed for EAER.

Selected summaries, as specified in Section 10.2.2, will include the risk difference between bimekizumab and secukinumab. The risk difference is calculated as:

$$RD = IP_{BKZ} - IP_{SEC}$$

where  $IP_{BKZ}$  is the incidence proportion for the bimekizumab-treated group and  $IP_{SEC}$  is the incidence proportion for the secukinumab group. Note that incidence proportion simply refers to the percentage of subjects within the specified treatment group that experienced a given adverse event.

The standard error for the risk difference is calculated as follows:

$$SE_{RD} = \sqrt{\left( IP_{BKZ} \times \left( \frac{1 - IP_{BKZ}}{n_{BKZ}} \right) \right) + \left( IP_{SEC} \times \left( \frac{1 - IP_{SEC}}{n_{SEC}} \right) \right)}$$

where  $n_{BKZ}$  is the number of subjects in the bimekizumab-treated group and  $n_{SEC}$  is the number of subjects in the secukinumab group.

The corresponding confidence interval for the risk difference is as follows:

$$CI_{RD} = RD \pm Z_{1-\alpha/2} \times (SE_{RD})$$

where  $Z_{1-\alpha/2}$  is the Z statistic for the corresponding level of alpha. For the risk difference confidence intervals calculated in this SAP, 1.96 will be used (corresponding to a two-sided alpha of 0.05 and 95% confidence interval).

Separate by-subject listings of all TEAEs for the OLE and the OLE2 treatment periods will be provided.

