The following summary will be provided by treatment for the Initial and Maintenance Treatment Period (combined) for the SS (only subjects treated with BKZ, only Total BKZ will be summarized):

- Incidence of TEAEs per 100 subject years by SOC, HLT, and PT and by Time of Onset Relative to Anti-bimekizumab Antibody Status

Incidence of TEAEs per 100 subject years by SOC, HLT, and PT and by Time of Onset Relative to COVID-19 pandemic (prior to COVID-19 pandemic, during COVID-19 pandemic).

The following summaries will be provided by treatment for the Initial Treatment Period (SS) as well as for Initial and Maintenance Treatment Period combined (SS):

- Incidence of TEAEs Above Reporting Threshold of 5% with Risk Differences by SOC and PT
- Incidence of Serious TEAEs and Risk Differences by SOC and PT

The tables with risk differences will also be accompanied by figures (dot plots) which show the incidence of the adverse events and corresponding 95% risk difference confidence intervals. These will be ordered by descending order of risk difference (bimekizumab vs secukinumab).

The following selected AEs summaries will be provided separately for the Open-Label Extension Period. Separate AEs summaries will be provided for the OLE2 treatment period by treatment sequence as described in Section 3.6 and will be based on the OLS2:

- Incidence of COVID-19 TEAEs
- Incidence of TEAEs Overview
- Incidence of TEAEs per 100 Subject-Years
- Incidence of Serious TEAEs per 100 Subject-Years
- Incidence of Serious TEAEs by Relationship
- Incidence of TEAEs Leading to Discontinuation per 100 subject-years
- Incidence of TEAEs Leading to Death
- Incidence of Non-Serious TEAEs Above Reporting Threshold of 5% by SOC and PT
- Incidence of Non-Serious TEAEs Above Reporting Threshold of 5% by Relationship SOC and PT

In addition, the following AEs summaries will be provided for the Open-Label Extension Periods only, by treatment at the time of AE onset, and will be based separately on the OLS and OLS2.

- Incidence of TEAEs Excluding TEAEs Exclusively Related to COVID-19 Vaccine by SOC, HLT, and PT
- Incidence of TEAEs Exclusively Related to COVID-19 Vaccine by SOC, HLT, and PT
- Incidence of COVID-19 Vaccine Interval Censored TEAEs by SOC, HLT, and PT
- Incidence of COVID-19 Vaccine Interval TEAEs by SOC, HLT, and PT

The following listings will be provided separately for the OLS and OLS2:

- Listing of TEAEs Related to COVID-19 Vaccine

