### 10.2.3 Other Safety topics of interest

The following summaries for AEs of other safety topics of interest will be provided by actual Treatment at the time of the adverse event. The following outputs will be produced separately for the SS for the initial treatment period, for the SS for the Initial and Maintenance Treatment Period, and for the OLS for the Open-Label Extension Period by treatment group (see Section 3.6). No safety topics of interest AE summaries will be produced for the Open-Label Extension 2 treatment period (OLS2).

Similar outputs for hypersensitivity events and hepatic events will also be produced for the Maintenance Treatment Period for the MS.

Additional analyses will be presented for subjects who switched from secukinumab to bimekizumab at Week 48 and the AEs will be assigned according to the onset date relative to last secukinumab dose and accounting for approximately 5 times half-life (Onset  $\leq$  140 days from last secukinumab dose or Onset  $>$  140 days from last secukinumab dose).

Along with the tables described, there will be tables which displays the risk difference and 95% confidence intervals for each of the topics of interest during the Initial Treatment Period (SS) as well as for Initial and Maintenance Treatment Period combined (SS). Corresponding figures (with dot plots) will be prepared.

Listings of all treatment emergent adverse events of other safety topics of interest will be provided separately for the OLE and the OLE2 treatment periods.

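### The Wald interval fixed for adverse-event risk differences has zero width when neither arm has an event, and understates possible excess harm when a rare event is nearly confined to one arm

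*SAP*

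**What the plan says.** Section 10.2.1 defines the risk difference as the bimekizumab incidence proportion minus the secukinumab incidence proportion. It gives the unpooled standard error ("The standard error for the risk difference is calculated as follows") and then fixes the multiplier: "For the risk difference confidence intervals calculated in this SAP, 1.96 will be used", described as "corresponding to a two-sided alpha of 0.05 and 95% confidence interval". There is no continuity correction and no alternative for zero or sparse cells.

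Two sections apply this interval to events that may be rare:

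- Section 10.2.2 lists "Incidence of Serious TEAEs and Risk Differences by SOC and PT" for the Initial Treatment Period and for the Initial and Maintenance periods combined. Dot plots go with these tables, ordered by risk difference.
- Section 10.2.3 says that "there will be tables which displays the risk difference and 95% confidence intervals for each of the topics of interest", for the same two periods and again with dot plots. The topics include opportunistic infections, MACE, suicidal ideation and behavior, and inflammatory bowel disease.

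The formula also serves the tables of events above the 5% reporting threshold. For incidence rates, Section 10.2.1 uses exact Poisson limits instead.

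**The concern.** The unpooled standard error is estimated from the observed proportions, so an arm with no event contributes no variance. If neither arm has an event, the standard error is zero and the display shows [0, 0] labelled as a 95% interval. If one arm has very few events and the other almost none, the estimated variance is too small exactly when the estimated difference is too small. The upper limit then falls below the true difference.

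An event nearly confined to one arm is the pattern that a drug-specific harm would produce. The tables and dot plots are where a reader judges how large an excess could still be. An upper limit that is too low understates it.

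**Working it through.** **Inputs.** The multiplier is 1.96 at two-sided alpha 0.05, with the unpooled standard error (Section 10.2.1). The planned size is 350 per arm (Section 2.4). The SAP states no adverse-event rates, so the true rates below are assumptions, taken from 0 to 10% per arm.

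**The plan's own figure.** The two-sided 5% normal quantile is 1.95996, which rounds to the stated 1.96. The multiplier is right. The question is the standard error that it multiplies.

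**Formula.** RD ± 1.96 × sqrt[p1(1 − p1)/n1 + p2(1 − p2)/n2], with p1 and p2 the observed proportions.

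**Sparse counts at 350 vs 350.**

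- 0 vs 0: both variance terms are 0, so the interval is [0, 0]. Newcombe gives −1.09% to +1.09%.
- 1 vs 0: p1 = 1/350 = 0.286%, and the interval is −0.27% to +0.84%. Newcombe gives −0.83% to +1.60%. One event in one arm is enough to remove the zero width.

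The chance of 0 vs 0 when both true rates are 0.1% is 0.999^700 = 49.6%. At 0.3% in both arms it is 0.997^700 = 12.2%.

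**Coverage.** For each pair of true rates, the probability of every pair of counts (two independent binomials) was summed over those whose interval contains the true difference.

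| True rates | Wald coverage | Upper limit too low |
|---|---|---|
| 0.3% vs 0 | 65.0% | 34.9% |
| 0.5% vs 0.1% | 82.5% | 17.3% |
| 1% vs 0.1% | 85.8% | 13.5% |
| 1% vs 0.3% | 93.0% | 6.0% |
| 1% vs 0.5% | 94.4% | 4.2% |
| 2% vs 1% | 94.8% | 3.6% |
| 0.1% in both | 99.9% | under 0.1% |
| 0.3% in both | 98.5% | 0.8% |
| 0.5% in both | 96.4% | 1.8% |
| 1% in both | 95.4% | 2.3% |
| 2% in both | 94.9% | 2.6% |
| 5% vs 3% | 94.9% | 2.9% |
| 10% vs 5% | 94.9% | 2.8% |

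The first three rows can be checked by hand.

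- At 0.3% vs 0 the upper limit misses whenever no event occurs: 0.997^350 = 34.9%.
- At 0.5% vs 0.1% it misses whenever the higher-rate arm has no event: 0.995^350 = 17.3%.
- At 1% vs 0.1% the true difference is 0.9%. It misses when the higher-rate arm has 0 or 1 events, because even 1 vs 0 gives an upper limit of only 0.84%. The probability is 0.99^350 + 350 × 0.01 × 0.99^349 = 0.030 + 0.105 = 13.5%.

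A symmetric 95% interval would put 2.5% on each side.

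**With the alternatives.** At the first three pairs of rates, Newcombe covers 98.4% to 99.99%. Miettinen-Nurminen covers 94.4% to 100% over the rates tried up to 3%.

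**Unequal arms.** After Week 16 the bimekizumab arm is "re-randomized 1:2 to receive bimekizumab 320mg Q4W or bimekizumab 320mg Q8W", about 350/3 = 117 and 2 × 350/3 = 233 subjects before dropout. If the combined-period risk differences were shown by regimen, Wald coverage at 1% in both arms would be 85.5% for 117 vs 350 and 93.7% for 233 vs 350. The SAP does not say that these tables are split this way, so the verdict does not rest on these figures.

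**The case against.** The strongest reply is that the problem is narrow. At 1:1 with equal true rates, the Wald interval covers 95.4% to 99.9% at rates of 1% or below and about 95% above that. With unequal rates it still covers 94.4% at 1% vs 0.5%. A reader might infer that the interval fails for rare events in general. The numbers do not support that, and this part of the reply stands. The large shortfalls need one arm at about 0.1% or less with a different rate in the other. The SAP does not say which events will look like that, and some topics, such as fungal infections or injection site reactions, need not be rare.

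A reader might also infer that the interval raises false alarms by excluding zero on a handful of events, for example at 4 vs 0. That does not follow. Wald gives +0.03% to +2.26% there, but Miettinen-Nurminen also excludes zero (score z = 2.004), while Newcombe does not. With equal true rates of 1% or below, Wald excludes zero in at most 4.6% of trials (100% − 95.4%).

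The reach of the zero-width case is limited too. A preferred-term row normally appears only once an event has been reported, so [0, 0] concerns mainly the predefined topic rows.

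Finally, sparse counts are not ignored everywhere. The topic summaries are per 100 subject-years, and Section 10.2.2 requires such summaries to carry the exposure-adjusted incidence rate with its exact Poisson interval. With no event, that upper limit is still −ln(0.025) = 3.69 events over the arm's exposure. This helps the reader within each arm. It does not correct the between-arm interval, which is the one plotted.

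**Conclusion.** The concern holds in a limited form. The prescribed interval is [0, 0] when neither arm has an event. It undercovers when a rare event is nearly confined to one arm: 65.0%, 82.5% and 85.8% at 0.3% vs 0, 0.5% vs 0.1% and 1% vs 0.1%. The error is almost entirely on the upper side, so possible excess harm is understated. For equal true rates, and for common events such as 5% vs 3%, coverage is about 95% or higher and the formula is adequate.

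These figures assume 350 per arm and adverse-event rates that the SAP does not state. A reader might take the point as a threat to the trial's conclusions. It is not one: the displays are descriptive, and the fixed-sequence procedure in Section 4.5 covers efficacy only. The change is still worth making, because these displays are labelled as 95% intervals and deliberately include serious events and safety topics.

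**What to change.** In Section 10.2.1, replace the Wald formula with a named score-type interval, Miettinen-Nurminen or Newcombe, for adverse-event risk differences. At minimum, do so for the serious-event tables in Section 10.2.2, the topic tables in Section 10.2.3 and their dot plots. Name one method, since the two can differ on sparse counts. The Wald formula could stay for events above the 5% threshold, but one method throughout is simpler to read.

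The cost is one formula in the SAP and one option in the program. Intervals become wider and slightly conservative for very rare events. At 1 vs 0, for example, the width goes from 1.12 percentage points (Wald) to 2.43 (Newcombe). For common events little changes.

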### 10.2.1.1 COVID-19 related data considerations

In order to assess the impact of the COVID-19 global pandemic on TEAEs, an additional AE summary based on the BKZ set will be presented for the combined Initial, Maintenance, and OLE periods. The following data considerations are introduced to support this presentation by the following periods:

- Prior to COVID-19 pandemic
- During COVID-19 pandemic

The COVID-19 pandemic start date is defined as 11 March 2020 as it is the date the World Health Organization declared COVID-19 as a pandemic, see also Section 4.2.1.7.2. Note that the Week 48 and Week 96 interim analyses will be conducted during the pandemic therefore a post COVID-19 pandemic period is not defined for these analyses. If WHO declares the COVID-19 pandemic has ended prior to Week 144, then that date may be used to support presentation of a post COVID-19 pandemic period.

Where a subject's time at risk includes 11 March 2020, the subject is included in the denominator for both periods and their time at risk is split as follows:

- Prior to COVID-19 pandemic:
  - Start of time at risk to 10 March 2020
- During COVID-19 pandemic:
  - 11 March to end of time at risk

Where a subject's time at risk does not include 11 March 2020, the subject is only included in the denominator for the Prior to COVID-19 pandemic period and their time at risk would be included entirely in the Prior to COVID-19 pandemic period.

Detailed definitions for subject time at risk are outlined in Section 10.1.

AEs are assigned to the appropriate period according to start date:

- Prior to COVID-19 pandemic:

- AE start date  $\leq$  10 March 2020
- During COVID-19 pandemic:
  - AE start date  $\geq$  11 March 2020

Incidence of COVID-19 TEAEs will be summarized for the OLE treatment periods based on the OLS by treatment group.

The following PTs will be used to identify COVID-19 related TEAEs. These will include confirmed and suspected COVID-19 infection:

- Corona virus infection
- Coronavirus test positive

By-subject listings of COVID-19 TEAEs will be produced separately for OLE and OLE2 treatment periods.

To assess the impact of COVID-19 mass vaccination on TEAEs, a sensitivity analysis will present all TEAEs excluding TEAEs assessed as exclusively related to COVID-19 vaccine by the investigator. TEAEs recorded as related to both study medication and COVID-19 vaccination should not be excluded. A complementary table of TEAEs related to COVID-19 vaccine will be presented.

Another sensitivity analysis will present vaccine interval censored TEAEs, that is all TEAEs excluding TEAEs with start date on or up to 5 days after date of COVID-19 vaccine. Note that subjects may receive more than one administration of COVID-19 vaccine. A complementary table and listing of vaccine interval TEAEs, that is TEAEs with start date on or up to 5 days after date of COVID-19 vaccine will also be presented.

Complementary listings of TEAEs related to COVID-19 vaccine will be presented for the OLE and the OLE2 treatment periods separately.

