During the OLE Period, subjects will attend study visits at Weeks 52, 56, 64, and 72, and then every 12 weeks. At study visits, IMP will be administered in the clinic by sc injection as applicable. In between study visits, subjects will self-inject IMP at home. Subjects who are unable to or decide not to self-inject IMP or those without a family member/friend/caregiver who can help, will not be discontinued, but may continue to visit the site for unscheduled visits for IMP administration only.

All subjects not enrolling in the Open-Label study will have the Week 48 study assessments and will enter the SFU Period.

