- Minimum and maximum will have the same number of decimal places as the original value.

Derived variables in general will display the mean, SD and median to 1 more decimal place than the variables used in the derivation. If the number of decimal places reported in the raw data is varied then use either the maximum raw number of reported decimal places or 3, whichever is the lowest, as a guide for the descriptive statistics.

Statistical tests of efficacy variables will be presented as two-sided p-values rounded to three decimal places. P-values less than 0.001 will be presented as “<0.001” and p-values greater than 0.999 will be presented as “>0.999.” Statistical comparisons will be two-sided and will be performed at the 0.05 level of significance.

Per protocol, visit windows of  $\pm 3$  days from the first dose to Week 24,  $\pm 7$  days from Week 28 to Week 72 and  $\pm 14$  days from Week 76 to Week 144 are permissible. For the SFU Visit, visit window is 20 weeks  $\pm 7$  days from final dose.

Per protocol, visit windows of  $\pm 14$  days from the first OLE2 dose at all OLE2 visits except SFU2 are permissible, the SFU2 visit window is 20 weeks  $\pm 7$  days from final dose in OLE2.

All by-visit summaries will contain nominal (i.e. scheduled) visits only. Unscheduled visits will not be mapped to scheduled visits except for assessments that occur within a 3-day time window of a scheduled visit. In that case, the assessment will be mapped to the corresponding scheduled visit and will be used for the analysis. This will only occur for some vendor data.

A complete set of data listings containing all documented data as well as calculated data (e.g. change from Baseline) will be generated. Separate data listings will be generated for the OLE2 period.

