#### **4.2.1.7 Missing data methods for assessing impact of COVID-19**

In order to assess the impact of the COVID-19 global pandemic on planned statistical analysis, additional sensitivity analyses will be performed for the secondary efficacy variable PASI100 response at Week 48. The sensitivity analyses in Section 8.2.3 will also still be performed, Assessments for the primary efficacy variable and for other secondary efficacy variables are at timepoints prior to Week 48 and will have been performed prior to the pandemic, therefore additional supplementary analyses of these variables are not necessary.

As described in Section 4.2.1, if a subject discontinues early from the study, all efficacy data that are collected later than 35 days after the last administration of study treatment will be treated as missing and subject to imputation as applicable. Thus if a subject discontinues from the study due to COVID-19 (general circumstances related to the COVID-19 pandemic or due to confirmed or suspected infection with the novel coronavirus) and the PASI assessment at Week 48 is later than 35 days after the last administration of study treatment, this will also be treated as missing.

If the PASI assessment at Week 48 is conducted by video call or telephone, this will be treated as missing since the validity and exchangeability of these assessment modalities has not been established. This will be determined according to collection of COVID-19 protocol deviations (including COVID-19 impact assessment) (see Section 3.4 for further details).

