#### 4.2.1.7.2 Subgroup approach for assessing the impact of COVID-19

A supplementary sensitivity analysis method to assess the impact of the COVID-19 pandemic on PASI100 response at Week 48 will use a subgroup analysis approach and will be based on the MS. The COVID-19 pandemic subgroups are defined as:

- Week 48 visit date before COVID-19 pandemic start date (ie, prior to COVID-19 pandemic)
- Week 48 visit date on or after COVID-19 pandemic start date (ie, during COVID-19 pandemic)

Where:

- COVID-19 pandemic start date is 11 March 2020. (The date is chosen as the date the World Health Organization declared COVID-19 as a pandemic.)
- For subjects with a Week 48 visit, the actual date of the Week 48 PASI assessment will be used to determine subgroup inclusion.
- For subjects without a Week 48 visit, the scheduled Week 48 visit date will be used to determine subgroup inclusion, where:
  - Scheduled Week 48 visit date = date of first dose of study drug + 336 days.

Note:

- It is not anticipated that there will be any Week 48 visits post-pandemic for this study.
- Although the COVID-19 pandemic subgroups are determined based on an event occurring after randomization, the inclusion of a subject in the applicable subgroup is independent of their PASI assessment at Week 48 and is independent of the subject's Baseline characteristics.

This subgroup analysis for PASI100 at Week 48 will include descriptive statistics with missing data imputed using NRI.

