- Listing of COVID-19 Vaccine Interval TEAEs

The following summaries will be provided for the BKZ Set by treatment at the time of AE onset. These tables will include AEs from both the double-blind and Open-Label treatment period (excluding OLE2 treatment period). AEs that occurred while subjects received secukinumab will not be included.

- Incidence of TEAEs Overview
- Incidence of TEAEs per 100 Subject-Years
- Incidence of Serious TEAEs per 100 Subject-Years
- Incidence of TEAEs by decreasing frequency of PT

- Incidence of TEAEs per 100 subject years by SOC, HLT, and PT and by Time of Onset Relative to COVID-19 pandemic (prior to COVID-19 pandemic, during COVID-19 pandemic).

In addition, all summaries of TEAEs based on “100 subject years” will include EAIR (with 95% CI) and EAER.

The following summaries will be presented for subjects who switched from secukinumab to bimekizumab at Week 48. The analyses will assign AEs according to the AE onset date relative to last secukinumab dose and accounting for approximately 5 times half-life (Onset  $\leq$  140 days from last secukinumab dose or Onset  $>$  140 days from last secukinumab dose):

- Incidence of TEAEs Overview
- Incidence of TEAEs per 100 Subject-Years
- Incidence of Serious TEAEs per 100 Subject-Years

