### 12.3 Appendix C: Week 96 interim analyses

An additional data cut will occur approximately after the final Week 96 visit, an interim analysis will be performed focused on the Open-Label extension treatment period.

The currently anticipated date for the final Week 96 visit is 19 March 2021. The interim analyses will include:

- Efficacy data through the Week 96 visit.
- Safety data through 19 March 2021.

Selected tables, figures and listings will be produced for this Week 96 interim analysis. Study population characteristics, demographics, other baseline characteristics and measurements of treatment compliance will be presented for the OLS. The following efficacy variables will be presented for the Open-Label extension treatment period based on the OLS, this will include presentations based on the subgroup of participants switching from secukinumab to bimekizumab:

- PASI90 response
- PASI100 response
- IGA Clear or Almost Clear (with at least a 2-category improvement from Baseline)

- IGA Clear (with at least a 2-category improvement from Baseline)
- Scalp IGA Clear or Almost Clear (with at least 2 category improvement relative to Baseline)
- Palmoplantar IGA Clear or Almost Clear (with at least a 2-category improvement from Baseline)
- DLQI total score of 0 or 1
- mNAPSI90, mNAPSI100
- Absolute, change, and percent change from Baseline in PASI score
- Absolute PASI scores of  $\leq 1$ ,  $\leq 2$ ,  $\leq 3$
- Absolute and percent change from Baseline in BSA affected by PSO
- Psoriasis BSA values of 0%,  $\leq 1\%$ ,  $\leq 3\%$
- PSD response (itch, pain and scaling)
- PSD 0 or 1 (itch, pain and scaling)
- PSD 0 (itch, pain and scaling)

The following safety variables will be presented for the Open-Label extension treatment period based on the OLS:

- Extent of exposure
- TEAEs including COVID-19 and safety topics of interest
- Laboratory data focused on TEMA and CTCAE
- e-CSSRS
- PHQ-9
- COVID-19 impact

Selected analyses of TEAEs will be presented for the subgroup of participants switching from secukinumab to bimekizumab for the Open-Label extension treatment period based on the OLS. Selected analyses of TEAEs will also be presented for the BKZ Set by treatment at the time of AE onset. These tables will include AEs from both the double-blind and Open-Label treatment period.

In addition, the following tables will be produced:

- Past psoriasis medication

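### The TEAE rates before and after 11 March 2020 cannot separate a pandemic effect from time on bimekizumab and visit schedule

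*SAP*

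**What the plan says.** Section 10.2.1.1 gives the aim as assessing the pandemic's impact on TEAEs, and for this "an additional AE summary based on the BKZ set will be presented for the combined Initial, Maintenance, and OLE periods". The cut is fixed: "The COVID-19 pandemic start date is defined as 11 March 2020". A subject whose time at risk spans the cut has it divided there. A subject whose time at risk does not include that date is placed wholly in the prior period. Events are assigned by their start date.

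Section 10.2.2 lists the table for the BKZ Set as TEAEs per 100 subject-years "by Time of Onset Relative to COVID-19 pandemic (prior to COVID-19 pandemic, during COVID-19 pandemic"), by treatment at onset, with the exposure-adjusted incidence rate (EAIR, with 95% CI) and event rate (EAER). The same split is listed for the combined Initial and Maintenance Period in the Safety Set, total bimekizumab only.

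Three other places fix the time structure:
- Section 12.3: "The currently anticipated date for the final Week 96 visit is 19 March 2021".
- Section 2.3.2.4: in the OLE, "subjects will attend study visits at Weeks 52, 56, 64, and 72, and then every 12 weeks".
- Section 4.2.1.7: the primary and other secondary efficacy assessments are at "timepoints prior to Week 48 and will have been performed prior to the pandemic".

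**The concern.** The two periods differ in more than the pandemic. Prior time contains nearly all early treatment, when subjects were seen often; the antibody samples in Section 9.3.2 are at Weeks 1, 2, 4, 8, 12 and 16. During time is mostly late treatment, with scheduled clinic visits every 12 weeks. Dividing by subject-years adjusts for how long subjects were followed, not for when in treatment that follow-up fell. The SAP plans no stratum for time since first bimekizumab dose, no matched window and no caution on interpretation.

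A lower rate after March 2020 could be taken for under-reporting or less infection when it reflects longer time on drug. A real rise could be hidden in the same way.

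**Working it through.** **Inputs from the SAP.** Cut date 11 March 2020 (10.2.1.1). Anticipated last Week 96 visit 19 March 2021 (12.3). A 14-day window either side at that visit (3.1: "days from Week 76 to Week 144 are permissible"). Seven-day weeks counted from first dose (4.2.1.7.2: "Scheduled Week 48 visit date = date of first dose of study drug + 336 days"). Secukinumab subjects start bimekizumab at Week 48 (2.3.2.4).

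**Step 1: check the SAP's statement on timing.** Last first dose = 19 March 2021 - 96 x 7 = 672 days = 17 May 2019 (3 to 31 May with the window). Adding 112 days gives a last Week 16 of 6 September 2019, or 20 September at the latest. That is before the cut, so the statement in Section 4.2.1.7 is reproduced for the Week 4 and Week 16 endpoints.

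**Step 2: where subjects stood at the cut.** From 17 May 2019 to 11 March 2020 is 299 days, or Week 42.7. For the randomized arm to have first-16-week time in the during period, a first dose after 20 November 2019 would be needed, and so a Week 96 visit after about 22 September 2021. The arm's first 16 weeks are therefore all prior.

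**Step 3: shares of person-time.** The SAP gives no enrolment dates. *Assumptions*: even enrolment from 1 June, 1 September or 1 November 2018 to 17 May 2019, equal arms, no dropout, everyone enters the OLE, time counted to Week 144 (1008 days). The September start, in mean days per subject:
- Bimekizumab arm: first doses lie 557 to 299 days before the cut, mean 428. Prior = 428, of which 112 early. During = 1008 - 428 = 580, none early.
- Secukinumab switchers: bimekizumab starts between 221 days before and 37 days after the cut, a spread of 258 days. Prior = (221²/2)/258 = 94.7, of which early = (112²/2 + 109 x 112)/258 = 71.6. During = 672 - 94.7 = 577.3, of which early = 112 - 71.6 = 40.4.
- Early share of prior = (112 + 71.6)/(428 + 94.7) = 35.1%. Early share of during = 40.4/(580 + 577.3) = 3.5%.
- Bimekizumab arm after Week 72 (504 days): prior (53²/2)/258 = 5.4 of 428 = 1.3%; during (504 - 5.4)/580 = 86.0%.

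**Step 4: ratio with no pandemic effect.** Let the first-16-week rate be k times the later rate. Then prior/during = [1 + (k-1) x early share of prior] / [1 + (k-1) x early share of during]. For the September start and k = 1.5: (1 + 0.5 x 0.351)/(1 + 0.5 x 0.035) = 1.16.

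| | June 2018 | Sept 2018 | Nov 2018 |
|---|---|---|---|
| Early share, prior / during | 32% / 3% | 35% / 3% | 37% / 4% |
| After Week 72 (bimekizumab arm), prior / during | 6% / 89% | 1% / 86% | 0% / 83% |
| Prior/during, k = 1 | 1.00 | 1.00 | 1.00 |
| Prior/during, k = 1.5 | 1.14 | 1.16 | 1.16 |
| Prior/during, k = 2 | 1.28 | 1.31 | 1.31 |

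**Step 5: the rule for time that misses the cut.** The last Week 48 is 17 April 2020, 37 days after the cut. With enrolment lasting 350, 258 or 197 days, 37/350 to 37/197 = 11-19% of switchers start bimekizumab after the cut. Taken literally, Section 10.2.1.1 puts their time in prior, while their events fall in during. For the September start the misplaced time is m = (37/258) x 672 = 96.4 days per switcher. With a constant rate, during/prior = [1157.3/(1157.3 - 96.4)] x [(522.7 + 96.4)/522.7] = 1.29. The three starts give about 1.2 to 1.4.

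**Step 6: the Initial and Maintenance split.** Mean double-blind time after the cut for the September start is (37²/2)/258 = 2.7 days, or 0.4 of 48 weeks. The three starts give 0.3-0.5 weeks, about 1%.

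**The case against.** A reader might infer that the two rates must differ by construction. The documents do not support that. What differs by construction is the mix of time on drug and visit schedule. The rates differ only if incidence or its ascertainment changes with time on drug, which the SAP never says. Under a constant rate the ratio is 1.00, and the values of k above are assumptions.

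Nor is the during period free of early bimekizumab time. That holds for the randomized arm only; switchers contribute the 3-4%.

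The direction cannot be predicted either. Taken literally, the rule in Step 5 pushes the during rate up, against any fall from longer time on drug.

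The SAP plans no test, ratio or decision rule for this table, and it gives TEAE rates separately for the Initial, Maintenance and OLE periods, which offers some context. How events are collected between visits is protocol content not shown here. Subjects who do not self-inject may also attend for extra dosing visits, so 12-weekly contact is not universal.

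These points limit the claim and its weight but do not remove it. Assessing pandemic impact is the table's only stated purpose, and as specified it cannot do that.

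**Conclusion.** The point holds as one of confounding: calendar period is strongly tied to time on bimekizumab and to visit schedule. That the randomized arm's first 16 weeks are all prior rests on the SAP's dates alone. The shares (about 32-37% against 3-4%) rest on the assumed enrolment and full retention. The ratios of 1.14-1.16 and 1.28-1.31 rest further on an assumed early excess and on time being split correctly. The conclusion is that the rates can differ with no pandemic effect and the table cannot separate the two, not that they will differ or in which direction.

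The mismatch between the time rule and the event rule for late switchers is a separate, concrete fault that must be put right for these rates to be valid. The Initial and Maintenance split has too little during time to inform. All of this concerns a supplementary safety summary and should be changed; no primary or key secondary conclusion depends on it.

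**What to change.** In Sections 10.2.1.1 and 10.2.2:
- Present the prior and during EAIR and EAER, at least for the overall TEAE and serious TEAE rows, by time since first bimekizumab dose (for example 0-16, >16-48 and >48 weeks), with the OLE also cut at study Week 72. A single stratum for study Weeks 48-96 would not do: in the bimekizumab arm, under the assumptions above, about 79-100% of its prior time lies in Weeks 48-72, against 30-38% of its during time. Switchers reach study Week 72 after 72 - 48 = 24 weeks on bimekizumab, so show them separately from the randomized arm.
- Base any statement on the pandemic only on strata with material time in both periods, and label the table descriptive.
- Count time at risk that starts on or after 11 March 2020 in the during period, to match the assignment of events by start date.
- Drop the split for the Initial and Maintenance Period alone.

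The cost is SAP wording, one stratification variable and a corrected derivation; no new data are needed. Some strata will be small and their intervals wide.
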